#### A. PRIMARY OBJECTIVES

- 1. To examine the positive predictive value of computerized CPT or ICD9 codes for SAB through medical record review for all cases combined and by maternal age and by code
- 2. To examine the accuracy of gestational age data in claims and in birth certificate data for the purposes of identifying pregnancy start among live delivery controls, who will be matched to chart-confirmed SAB cases

3. To examine the accuracy of potential confounders in claims data for the purposes of matching SAB cases and live delivery controls

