If there are sufficient control numbers, we will consider matching controls to cases on diagnoses of diabetes, obesity, asthma, and multiparity based on CPT and ICD9-coded data. Finally, where information on particular time-varying confounders is available in claims-based data, we will attempt to match cases and controls on such factors if sufficient controls exist. We will attempt to match cases and controls on the presence of urinary tract infections, respiratory infections, gastrointestinal infections, sexually transmitted infections, and medically attended fever within a 1-28 day period prior to SAB/index date, identified using ICD9-coded data (Appendix 5). Finally, we will collect information from the medical record on factors not matched upon in the design phase, such as smoking, alcohol, and substance abuse, and adjust for them in regression models if feasible.

Multiparity will be identified using codes listed in Appendix 5. The algorithms for identifying obesity and diabetes are described in the PRISM Influenza Vaccines and Birth Outcomes Protocol. Asthma will be identified using an algorithm validated and developed by the Medication Exposure in Pregnancy Risk Evaluation Program (MEPREP), an FDA-sponsored collaboration between 11 health plans. To be considered asthmatic, a woman must have one of the following during the 90 days prior to pregnancy through end of pregnancy: (1)>=2 outpatient visits at least 30 days apart with ICD9 diagnosis code 493\*, (2) >=1 inpatient visit with ICD9 diagnosis code 493\*, or (3) >=1 outpatient visit with ICD9 diagnosis code 493\* and >=1 dispensing of an asthma medication (short- or long-acting beta-agonist, inhaled corticosteroid, leukotriene receptor antagonist, mast cell stabilizer, methylxanthine). This algorithm was shown to have a positive-predictive value of 95% in MEPREP.

Among potential controls meeting matching and enrollment criteria, TIV identified in claims or IIS data must be received between -6 weeks gestation and 2 weeks past the case's gestational age at SAB, with gestational age estimates from birth certificate or infant-claims based estimates. A 2-week margin before and after the gestational period of interest will be initially incorporated to allow for misclassification of gestational age in live delivery controls due to use of claims and birth certificate data for gestational age estimates.

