#### I. IDENTIFYING POTENTIAL CONTROLS IN CLAIMS-BASED AND ADMINISTRATIVE DATA (PHASE 3 AND 4)

After 2 or more potential controls are identified in electronic data for each chart confirmed case, we will then conduct a second round of chart review to confirm that these controls have vaccine exposure in the gestational period of interest (i.e., 4 weeks before pregnancy start to the index date). These potential controls will proceed to full chart review to confirm live delivery, gestational age at delivery, pregnancy start date, TIV exposure, and gestational age at vaccination. Controls will only be retained if they received TIV between -4 weeks gestation and the index date. Initially we will require controls to be continuously enrolled in the 360 days prior to delivery. This 360-day period incorporates a 90-day period prior to pregnancy start and a 270-day period, the average gestational length of a term pregnancy. Following chart review, controls will only be retained if they are determined to have enrollment 90 days prior to pregnancy start through the index date. Following chart review, if both controls in a given case-control set do not meet inclusion criteria, we will attempt to match the case to an unmatched control from a different case-control set, if available. If cases remain unmatched despite these attempts, they will only be included in analyses for Objectives 1 and 2. If both controls in a given case-control set meet inclusion criteria, we will randomly select one control.

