#### K. CASE-TIME-CONTROL DESIGN

As proof-of-concept, a case-time-control study design will be implemented to examine whether risk of SAB is elevated in specific time periods following TIV or in specific gestational periods following TIV. We will identify SAB cases that were vaccinated between -4 weeks gestation until the date of the SAB. Since the likelihood of receiving TIV differs by gestational age and calendar time, we will match each case to a vaccinated control based on Data Partner, maternal age, and pregnancy start, where the control must have received TIV between -4 weeks gestation and the case's gestational age at SAB. In order to understand the feasibility of using the case-time-control design in Mini-Sentinel, we will first examine (1) the validity of claims data for identifying SAB; (2) the validity of birth certificate and claims data for identifying start among live delivery controls for matching them to chart-confirmed cases; and (3) the validity of using claims data for matching cases to controls on confounders, if matching on factors other than DP and pregnancy start is ultimately implemented. The details of the descriptive statistics for Primary Objectives 1-3, which will be used to address each of these aims, are described further in the analytic section of the protocol.

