#### O. MEDICAL RECORD REVIEW OF SAB CASES AND LIVE DELIVERY CONTROLS

All SAB cases will be adjudicated by an obstetrician or other physician (e.g., family physician) with experience in providing obstetric care to confirm SAB and estimate the dates of SAB and pregnancy start. SAB cases will be considered to be confirmed if intrauterine pregnancy (via, ultrasound or other clinician documentation) and natural pregnancy loss prior to 20 weeks gestation is documented in the medical record. For a sensitivity analysis, we will consider collecting information on the presence of congenital anomalies that may affect fetus viability from the medical record, to be excluded both among cases and controls. We will also consider conducting another sensitivity analysis that excludes cases with medical record documentation of a blighted ovum (also called an embryonic gestation), and their

matched controls, if numbers permit. In addition, information on potential risk factors for SAB, including asthma, gravidity, prior history of SAB, diabetes, febrile illness, medically attended infections, and obesity, will be collected primarily for descriptive purposes. If feasible, we will adjust for smoking, alcohol, and substance abuse in regression models, using information from the medical record.

All SAB events estimated to have occurred prior to 6 weeks gestation will be excluded since recognition of pregnancy loss prior to this point is uncommon and thus it is difficult to establish date of pregnancy start and date of SAB. Potential cases or controls for whom it is determined that TIV did not occur between -4 weeks gestation and the case's gestational age at SAB event (i.e., the study period of interest) will also be excluded.

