In Primary Objective 3, we will determine the accuracy of claims data for matching potential cases and controls on potential confounders. We will determine the positive predictive value in cases and controls for each of the confounders matched upon. We will also determine the proportion of matched case-control pairs that have concordant status in chart data for each matching factor (i.e., confounder).

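### Cases left without a control are barred from all of Objective 3, although its positive predictive value in cases needs only the case's own claims and chart

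*Protocol*

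**What the plan says.** Section III.I describes what happens after control charts are reviewed. A rescue comes first: "if both controls in a given case-control set do not meet inclusion criteria, we will attempt to match the case to an unmatched control", drawn from another set. If that fails, the rule is: "If cases remain unmatched despite these attempts, they will only be included in analyses for Objectives 1 and 2".

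Section II.A words Objective 3, a primary objective, as: "To examine the accuracy of potential confounders in claims data for the purposes of matching SAB cases and live delivery controls". Section IV.A gives it two measures:

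- The first is a predictive value, measured on persons: "We will determine the positive predictive value in cases and controls for each of the confounders matched upon".
- The second is a concordance measure, and its unit is the pair instead of the person: "We will also determine the proportion of matched case-control pairs that have concordant status in chart data for each matching factor".

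Section III.O places the risk-factor information in the medical record review of cases and controls: the factors, "including asthma, gravidity, prior history of SAB, diabetes, febrile illness, medically attended infections, and obesity, will be collected primarily for descriptive purposes".

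Objective 3 is conditional. Section III.K has it apply "if matching on factors other than DP and pregnancy start is ultimately implemented", and section III.H makes comorbidity matching depend on supply: "If there are sufficient control numbers, we will consider matching controls to cases on diagnoses of diabetes, obesity, asthma, and multiparity". Matching on infections and fever is likewise to be attempted if enough controls exist.

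**The concern.** The two measures of Objective 3 have different units. Concordance is defined on pairs and cannot be computed without a control. The PPV in cases is defined on persons: among cases with a claims code for, say, asthma, it is the share whose chart confirms asthma. Whether a control survived review for dating or vaccination has no part in that calculation. Section IV.A itself names matched pairs for concordance and sets no such limit on the PPV.

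Section III.I nevertheless applies one exclusion to the whole objective. At stake is the number of coded-positive cases behind each confounder PPV. With a target of 100 cases, an uncommon condition may yield only a handful, so each one lost counts. A smaller problem is that the denominator depends on where the analyst looks: section IV.A read alone would include these women, and section III.I takes them out.

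**Working it through.** **1. What each measure needs.** The protocol states no expected PPV, precision or unmatched rate for Objective 3, so there is no planned figure to reproduce. The check is one of requirements.

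| Measure (IV.A) | Unit | Retained control needed? | Unmatched cases under III.I |
|---|---|---|---|
| Objective 3, PPV in cases | case | no | excluded |
| Objective 3, PPV in controls | control | not applicable | not applicable |
| Objective 3, concordance | matched pair | yes | excluded, necessarily |

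The reasons for dropping a control in III.I and IV.A are live delivery, pregnancy start, vaccination timing and enrollment. None bears on whether the case's own code is correct.

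**2. How many cases might be unmatched (assumed rates).** If each of k controls fails review independently with probability q, all fail with probability q^k, before any rescue match.

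- k = 2: q = 0.1, 0.2, 0.3, 0.4 gives 1, 4, 9, 16 per 100 cases.
- k = 6, the maximum in III.A and III.H: even q = 0.5 gives 0.5^6 = 1.6 per 100.

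The share may therefore be very small or appreciable. With two controls, 20% unmatched requires q = √0.20 = 0.45 and no successful rescue, which is towards the pessimistic end.

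**3. Effect on the PPV in cases.** Assume N = 100 confirmed cases, coded prevalence p, unmatched share u unrelated to coding, and PPV 0.90. The denominator is n = N × p × (1 − u). Wilson 95% intervals use expected counts, so some are not whole numbers.

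| p | u | n under III.I | Wilson interval | n if kept | Wilson interval |
|---|---|---|---|---|---|
| 5% | 30% | 3.5 | 0.39–0.99 | 5 | 0.46–0.99 |
| 10% | 10% | 9 | 0.58–0.98 | 10 | 0.60–0.98 |
| 10% | 20% | 8 | 0.56–0.98 | 10 | 0.60–0.98 |
| 20% | 10% | 18 | 0.69–0.97 | 20 | 0.70–0.97 |

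For p = 10% and u = 20%: 100 × 0.10 × 0.80 = 8, against 100 × 0.10 = 10.

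Whatever p and the PPV, the standard error √(PPV(1 − PPV)/n) grows by 1/√(1 − u): 5% at u = 10%, 12% at u = 20%, 20% at u = 30%.

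**4. What stays the same.** Concordance is unaffected, since an unmatched case cannot contribute to it. The pilot case-time-control and scan analyses are also unaffected.

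**The case against.** The strongest reply is that the sections do not conflict. IV.A is silent on unmatched cases and III.I supplies the rule. Objective 3 concerns accuracy for the purpose of matching, so reporting both measures on one matched set is coherent. It is true that the text can be followed as written. But matching uses claims data before control charts are opened, so accuracy for matching concerns the cases that enter matching, not only those whose controls later pass. Coherence does not make the exclusion necessary.

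It can also be said that Objective 3 is conditional and descriptive, with no precision target or decision threshold, and that rescue matching and up to six controls may leave few cases unmatched. All of this stands, and it limits the point to a minor one.

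Two stronger readings are tempting. A reader might infer that the charts are thrown away; they are not, since III.I keeps these cases in Objectives 1 and 2. A reader might also infer that women with a coded confounder are the likeliest to be lost, because matching on the condition narrows their pool of candidate and replacement controls. That is possible, but the documents give no rates to test it, the listed reasons for control failure do not involve confounders, and confounder matching is to be used only when controls are plentiful.

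**Conclusion.** The exclusion of unmatched cases from Objective 3 is justified for pair concordance and unnecessary for the PPV in cases. If confounder matching is implemented, the rule leaves usable case charts out of part of a primary objective.

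The consequence is lost precision, of unknown and probably modest size. Under the illustrative assumptions (100 confirmed cases, 10% coded, 20% unmatched, PPV 0.90) the denominator is 8 rather than 10 and the lower Wilson limit is 0.56 rather than 0.60. With fewer unmatched cases the difference nearly disappears; with rarer conditions it matters more.

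No bias in the PPV follows from the documents. Bias would require that ending unmatched be related to whether the code is true, and nothing in the protocol indicates this.

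**What to change.** Replace the sentence in section III.I with wording to this effect: cases that remain unmatched are included in Objective 1, in the control-discard proportions of Objective 2, and in the positive predictive values in cases of Objective 3; only the pair-concordance analysis of Objective 3 and the pilot objectives are limited to matched sets. Section IV.A can then stand, ideally with the denominator of each Objective 3 measure stated beside it.

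The cost is one sentence. Case charts are reviewed before controls are matched, and section III.O already collects the risk factors at record review. No further charts are needed, provided those factors are abstracted for every confirmed case at that review.

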### **III. STUDY DESIGN**

#### A. OVERVIEW OF CASE-TIME-CONTROL DESIGN

In this protocol, our main objective is to optimize algorithms for using claims and birth certificate data for studies of pregnancy outcomes. As proof-of-concept, we will also determine the feasibility of implementing a case-time-control design to examine whether risk of SAB is elevated within 1-28 days post-TIV or whether the risk is increased after TIV received between -4 to 4 weeks gestation, between 2 to 6 weeks gestation, or between 6 to 11 weeks gestation. We will match cases and controls (at least two controls per case, up to a maximum of 6) on Data Partner, maternal age, and pregnancy start date (i.e.., date of last menstrual period (LMP), pregnancy start based on ultrasound dating, or pregnancy start based on assisted reproductive technology; see methods for determination). Matching on pregnancy start in cases and controls will address temporal patterns in vaccination by seasonality and gestational age. If feasible, we will also attempt to match cases and controls on comorbidities, infections, and other potential confounders, which will maximize the comparability between cases and controls with respect to underlying time trends in exposure.

The case-time-control design is a variant of a case-cross-over study (CCO). The CCO study and its variants are especially well-suited to measuring transient effects of exposures on immediate risk of illnesses with abrupt onset. In a CCO study, in individuals who have experienced the outcome of interest, a comparison is made between the odds of exposure in a predefined risk interval to that in a self-matched comparison interval. In addition to using cases as the CCO study does, the case-time-control design also uses an external group of controls sampled from the same population that produced the cases to adjust for time trends in exposure (e.g., seasonality or gestational age at vaccination). As in the cases, in the controls, the odds of exposure is compared between the predefined risk and self-matched control interval to estimate the exposure trend bias; the odds ratio in cases is divided by the odds ratio in controls to produce an effect estimate for the association between exposure and outcome while adjusting for time trends in exposure.

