Because analytical formulas are not available to estimate the variances of scan statistics, we will use Monte Carlo simulation to obtain p-values. First 9999 random data sets will be generated under the null hypothesis. The null hypothesis is that the vaccination times of each case and its matched control are interchangeable and independent of the case/control status. Therefore, conditioned on the two vaccination times in each matched pair, we will randomly assign one of the two vaccination times to the case and the other to the control for each data set. For each random data set, we will calculate the most likely cluster in the same way as for the real data. The Monte Carlo p-value for the cluster in the real data set will then be calculated using the formula p = R / (1 + number of simulations) = R / (10,000), where R is the rank of the maximum likelihood from the real data set. For example, if there were only 17 random data sets with a maximum likelihood larger than the maximum likelihood from the real data set, then R=18 and p=0.0018. The calculations will be performed using SAS and the free SaTScan software for the spatial and space-time scan statistics (www.satscan.org).

For each scan statistic analysis, the result reported will be the start and end time of the most likely cluster, its p-value and it observed relative risk. However, one limitation of calculating the relative risk is that it may be overestimated if the scan is underpowered.

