#### **B. LIMITATIONS**

Foremost, we will have limited power to detect small or modest effect sizes in this feasibility study. For example, our target sample size of 100 cases and 100 controls corresponds to approximately 80% power to detect a relative risk of 2.4 or above for the pilot objective of examining whether there is an elevated risk with exposure during the risk interval of 2-6 weeks gestation. Of note, this power calculation may be somewhat optimistic if we obtain fewer charts than originally anticipated or if a significant portion of cases or controls do not meet study inclusion criteria (e.g., not vaccinated during the period of interest), or depending on the distribution of cases and controls in 3 different gestational age risk periods. Our power calculation may also be an overestimate if our assumptions used to calculate power, such as the gestational age distribution of SAB or the gestational distribution of vaccination among controls (both of which are based on published literature), are incorrect. However, the primary objectives of this proof-of-concept protocol are to determine optimal algorithms for using claims and birth certificate data for pregnancy related studies. As such, this study will have the capability to inform future studies on pregnancy outcomes in the Mini-Sentinel.

The current study's case definition is limited to women seeking medical care for SAB. A large percentage of miscarriages occur without medical care, particularly in those occurring early during pregnancy. A significant proportion of these early pregnancies, particularly in the first six weeks, are unrecognized by the mother, making detection difficult. Thus, results may not be applicable to the effects of vaccines on

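### Randomly dropping a second chart-confirmed control gives up as much as 10 points of power in the pilot regressions, more plausibly about 4 to 8

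*Protocol*

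**What the plan says.** Section III.I sends two or more electronically identified controls per case to full chart review, covering live delivery, dating, vaccination and gestational age at vaccination. If none qualifies, the case may take an unmatched control from another set. If two qualify: "If both controls in a given case-control set meet inclusion criteria, we will randomly select one control".

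The intended ratio differs between sections:

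- III.A: "at least two controls per case, up to a maximum of 6".
- III.E: two potential controls are sought per case, with at least one in the final analysis.
- III.H: one or more, up to six.
- III.I: a single control after random selection, with no rule for sets in which three to six were reviewed.
- III.K: each case is matched to one vaccinated control.

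Section IV.B specifies conditional logistic regression stratified by case:control set. Section IV.C writes the scan permutation for pairs: "we will randomly assign one of the two vaccination times to the case and the other to the control for each data set". Section V.B gives the only power figure: "our target sample size of 100 cases and 100 controls corresponds to approximately 80% power to detect a relative risk of 2.4 or above". It refers to the 2-6 week gestational interval, one of three intervals in Pilot Objective 5.

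**The concern.** When the random selection takes place, both controls have been reviewed and found eligible, so the cost has been met. The section gives no reason for dropping one. A likelihood stratified by matched set takes sets of different sizes as they come, so the regression gains nothing from forcing pairs.

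What is at stake is precision in the pilot case-time-control estimates, where section V.B itself warns that charts or eligible women may fall short. The result also comes to depend on an arbitrary draw between two equally valid controls.

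**Working it through.** **Inputs.** From the protocol: 100 cases and 100 controls, about 80% power, relative risk 2.4 (V.B); 140 potential cases for 100 final cases (III.E); average length of 10 weeks for pregnancies ending in miscarriage (III.F). Not in the protocol, so assumed: two-sided 5% level; 2.4 read as the odds ratio for vaccination in the risk interval; p0, the probability that a control was vaccinated in that interval, independent within sets.

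**Method.** For a set with M controls the score is U = x(case) − S/(M+1), where x = 1 if vaccinated in the risk interval and S is the number so vaccinated in the set. With p1 = 2.4·p0/(1 + 1.4·p0),

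power = Φ{[√n·E(U) − 1.96·√V0] / √Var(U)},

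where V0 is the mean of (S/(M+1))(1 − S/(M+1)). M = 1 is the McNemar test.

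**Stated figure (1:1).** Solving for 80% gives p0 = 0.226 and p1 = 0.412.
- E(U) = 0.0931, V0 = 0.1130, Var(U) = 0.1044.
- (10 × 0.0931 − 1.96 × 0.336)/0.323 = 0.84, so power is 80%.

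The stated figure is attainable, but it cannot be strictly reproduced without p0 and the significance level.

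**Every case keeps two controls (1:2).** Same p0.
- E(U) = 0.1241, V0 = 0.1394, Var(U) = 0.1466.
- (10 × 0.1241 − 1.96 × 0.373)/0.383 = 1.33, so power is about 91%.

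The odds ratio detectable at 80% power falls from 2.40 to about 2.12. As a check near the null, the variance ratio is (1 + 1/2)/(1 + 1) = 0.75.

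**Some controls fail review.** If each of two controls survives with probability q, the share of matched cases with two is q²/[1 − (1 − q)²] = q/(2 − q). Averaging the score terms over the two set sizes, for 100 matched sets:

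| q | Share with two | Power | Gain |
|---|---|---|---|
| 0.50 | 33% | 84.5% | 4.5 |
| 100/140 = 0.71 | 56% | 87.0% | 7.0 |
| 0.80 | 67% | 88.1% | 8.1 |
| 1.00 | 100% | 90.8% | 10.8 |

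Simulation of the stratified score test at the same p0 gave 81.0%, 85.3%, 87.5%, 88.7% and 91.2% for q = 0 (all 1:1), 0.50, 0.71, 0.80 and 1.00, in line with these values.

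**Reassignment.** The table ignores spare controls moved to unmatched cases. At q = 0.71, 51% of cases have two valid controls, 41% one and 8% none. If every unmatched case could be served, 51 − 8 = 43% would keep two, with power 85.7% (gain 5.7). At q = 0.50 the split is 25/50/25, and complete reassignment would leave no surplus. Complete reassignment is unlikely if the matching on Data Partner, age and pregnancy start still has to hold.

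**Other values of p0.** If vaccination were uniform over the 14 weeks from −4 to 10, p0 would be 4/14 = 0.286 or 5/14 = 0.357, depending on how the interval's end weeks are counted. Power then goes from 83.7% to 93.1%, or from 85.5% to 94.2%: about 9 points if all sets are 1:2, and about 6 at q = 0.71. A one-sided 5% test anchored at 80% (p0 = 0.149) goes to 89.8%.

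**The case against.** The strongest defence is that the design is 1:1 by intent. III.K, the scan permutation and the 100:100 target all point to pairs, so the second chart is a reserve against failed reviews. That reserve is partly used: spare controls can serve unmatched cases, and reviewed controls also inform Primary Objective 2. This stands as an account of the design and reduces the mismatch with III.A to a matter of wording. It does not explain why a surplus eligible control should be left out of a regression that can use it.

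The second argument concerns the scans, and it stands. The Bernoulli statistic in IV.C pools sets and compares the case fraction inside and outside each window. Under the null, pairs give an expected case fraction of 1/2 in every window; a set with two controls gives 1/3. A control must be vaccinated before the case's index date, so the number of valid controls may rise with gestational age at miscarriage, and the case fraction would then vary across windows without any effect. Drawing the case's time from all times in the set would keep the p-value valid, but would not correct the choice of cluster or the reported relative risk.

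Four stronger readings are tempting and not supported:

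- That 10 points is the expected loss. It requires two valid controls for every case, and the protocol plans for attrition.
- That all but one of up to six controls are discarded. The sentence covers only sets where both of two controls qualify.
- That the rule biases the estimate. Random selection among eligible controls costs precision only.
- That the primary objectives suffer. The power figure concerns one interval of one pilot objective.

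**Conclusion.** The concern holds as an efficiency loss in the pilot regressions (Objectives 4-5). The ceiling is about 10 points of power, from 80% to about 91%. About 4 to 8 points is realistic if between half and four-fifths of controls survive review, and less to the extent that spare controls are reassigned. These sizes rest on an assumed two-sided 5% test, about 22% of controls vaccinated in the 2-6 week interval, and 2.4 read as an odds ratio. The direction does not depend on those values: wherever a surplus confirmed control exists, keeping it adds information to the regression. Separately, the five sections that state a control ratio do not agree.

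**What to change.** 1. In III.I, replace the random selection for Objectives 4-5: offer spare confirmed controls first to cases left without one, as the section already allows, then keep all remaining confirmed controls in their set and fit the conditional logistic regression with a variable 1:M ratio.
2. For Objectives 6-8, keep one randomly selected control per case, unless the scan statistic itself, and not only its permutation, is adapted to varying set sizes.
3. Reconcile the control ratio in III.A, III.E, III.H, III.I and III.K, and state what happens when more than two controls are confirmed.
4. In V.B, restate the power with its assumed exposure prevalence among controls, significance level and sidedness, and expected control ratio.

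The cost is wording and a recalculated power statement, with no further charts. The one drawback is that the regressions and the scans would use slightly different control sets, which the report should say.
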